#### **10.3.5 Severity**

The investigator will assess each AE as either MILD, MODERATE, or SEVERE using the following guidelines to describe the maximum severity of the AE:

MILD: Does not interfere with subject's usual function

MODERATE: Interferes to some extent with subject's usual function

SEVERE: Interferes significantly with subject's usual function

Note that a **severe** AE is not necessarily a **serious** AE. For example, a headache may be severe in intensity, but would not be classified as serious unless it met 1 of the criteria for serious events listed above.

#### **10.3.6 Follow-up of Unresolved Events**

All AEs will be followed until they are resolved or the investigator assesses them as chronic or stable or the subject's participation in the trial ends (i.e., until a final report is completed for that subject).

In addition, all SAEs and those nonserious events assessed by the investigator as related to the study drug will continue to be followed even after the subject's participation in the trial is over. Such events will be followed until they resolve or until the investigator assesses them as "chronic" or "stable". Resolution of such events is to be documented on the appropriate CRF.

### **10.4 Exposure In-Utero**

A pregnancy in a female subject will be confirmed by a positive serum  $\beta$  human chorionic gonadotropin test.

The study drug will be immediately discontinued once the pregnancy of a female study participant has been confirmed.

If any study participant becomes or is found to be pregnant while receiving a study drug (vadadustat or epoetin alfa) or within 30 days of discontinuing the study drug, the pregnancy will be recorded on the Pregnancy Reporting Form/Exposure in Utero Form in EDC within 24 hours of awareness of the pregnancy or the investigator will call the CRO SAE hotline within 24 hours of being made aware of the pregnancy.

Pregnancy during this time frame of the female partner of a male subject will also be reported.

The Pregnancy Reporting Form/Exposure in Utero Form will be completed with all known information regarding the pregnancy at the time of reporting. Study site personnel will update the form with additional information regarding the pregnancy and the outcome of the pregnancy as it becomes available until the outcome of the pregnancy is reported.

The investigator will follow the subject (or female partner of a male subject) until completion of the pregnancy. If the outcome of the pregnancy meets the criteria for classification as an SAE (i.e., spontaneous abortion, stillbirth, neonatal death within 1 month of birth, or congenital anomaly [including that in an aborted fetus]), the investigator will also follow the procedures for reporting an SAE within 24 hours of awareness. A pregnancy in and of itself is not considered an AE; however, unexpected complications are considered AEs.

Additional information about pregnancy outcomes follows:

- Note that “spontaneous abortion” includes miscarriage and missed abortion.
- All neonatal deaths that occur within 1 month of birth will be reported, without regard to causality, as SAEs. In addition, any infant death after 1 month that the investigator assesses as related or unrelated to the in utero exposure to the study drug will also be reported.
- In the case of a live birth, the “normality” of the newborn can be assessed at time of birth.
- The “normality” of an aborted fetus can be assessed by gross visual inspection unless there are pre-abortion laboratory findings suggestive of a congenital anomaly.

## 10.5 Special Situations

Certain safety events, called ‘Special Situations’, that occur in association with study drug may require reporting. These Special Situations include, but are not limited to, the following:

- Overdose of the medicinal product
  - Epoetin alfa overdose – The US PI will be referenced for information on epoetin alfa overdosing.
  - Vadarustat overdose – There is no known antidote for vadarustat. In cases of suspected overdose, subjects will be treated per standard medical practice based on the investigator’s judgment and dose delays and reductions may be implemented as necessary.

Chronic overdosage with vadarustat may result in excessive production of red blood cells and polycythemia. Polycythemia can be potentially life threatening and may result in severe thrombosis and death (known as hyperviscosity syndrome). If hyperviscosity syndrome is observed, vadarustat will be discontinued and standard treatment for polycythemic hyperviscosity syndrome will be initiated (i.e., phlebotomy).

- Suspected abuse/misuse of the medicinal product
- Inadvertent or accidental exposure to the medicinal product
- Medication error involving the medicinal product (with or without subject exposure to the sponsor’s medicinal product [e.g., name confusion])
- Drug-drug interaction.

Special situations will be reported on the Special Situations CRF whether they result in an AE/SAE or not. Special situations with associated AE/SAE will also be reported on the corresponding AE/SAE forms, following applicable AE or SAE process.

## **10.6 Safety Monitoring**

This is an open label study allowing the study team full access to safety data which will be reviewed on a regular basis, throughout the course of the study. Safety monitoring will be performed as described in the Medical Monitor Plan.

## 11 DATA ANALYSIS

Data collected throughout the study will be summarized using descriptive statistics and listed in the by-subject listings. Continuous variables will be summarized using number of subjects with mean, standard deviation (SD), median, minimum, and maximum. For categorical variables, the number and percentage of subjects in each category will be tabulated. Summaries will be provided by treatment group within appropriate analysis populations (as defined in Section 11.2, Study Analysis Populations) and by time point/time period, as appropriate.

### 11.1 Sample Size Estimation

Approximately 95 subjects are planned for enrollment in the Main study with 40 and 55 subjects randomized to the low epoetin alfa dose group and the high epoetin alfa dose group, respectively. Approximately 30 subjects are planned for enrollment in the ESA hyporesponder parallel study.

Sample size reflects the exploratory nature of this study.

Enrollment may be increased by up to approximately 20 additional subjects in the Main study and by up to approximately 30 additional subjects in the ESA hyporesponder parallel study to ensure adequate data are captured for the primary, PK/PD, and safety endpoints.

### 11.2 Study Analysis Populations

The following analysis populations will be used in this study:

- Randomized population: defined as all randomized subjects. Analyses of this population will be based on the randomized treatment.
- Full Analysis Population (FAS): all subjects in the randomized population who received at least one dose of study drug and had at least one Hb assessment during the primary efficacy evaluation period. Analyses of this population will be based on the randomized treatment.
- Safety Population: all subjects in the randomized population who received at least one dose of study treatment. Analysis of this population will be based on the actual treatment received. Subjects who received in error some vadadustat and some epoetin alfa will be classified by the more frequently received drug.
- Per protocol (PP) population: all randomized subjects who received study drug during the primary evaluation period, had at least one Hb assessment during the primary efficacy evaluation period, received no rescue therapy (with ESA or transfusion) prior to the evaluation period, and had no major protocol deviation affecting the primary endpoint analyses. Major protocol deviations leading to exclusion from the PP population will be specified prior to database lock and recorded in a separate document. Analyses of this population will be based on actual treatment received.

Efficacy analyses will utilize the Randomized, Full Analysis, and PP Populations while safety analyses will utilize the Safety Population.

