### 5.3 Efficacy Endpoints

#### 5.3.1 Primary Endpoints

The primary endpoint will be the mean change in Hb between Baseline (average pretreatment Hb) and the primary evaluation period (average Hb from Weeks 10 to 12).

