##### **8.4.5.2 Transition of Vadarustat Once Daily Dosing to TIW Dosing Regimen**

All subjects randomized to vadarustat who complete 12 weeks of once daily dosing regimen **and** who meet all the Week 12 criteria below will be transitioned to a TIW vadarustat dosing regimen.

Week 12 Transition criteria:

- Vadarustat daily dose of 600 mg or lower at Week 12
- Hb within target range of 10.0 to 11.0 g/dL, inclusive, at Week 12 confirmed by central laboratory Hb value from Week 11 (11 weeks of treatment completed)
- No receipt of rescue therapy (ESA or RBC transfusion) for worsening of anemia due to CKD from Baseline/Day 1 to Week 12.
  - ESA or RBC transfusion prior to Week 12 for reasons unrelated to worsening of anemia due to CKD (e.g., surgery, gastrointestinal bleed, or inadvertent administration) is not considered rescue therapy

- No other reason, based on the investigator's clinical discretion that would make the subject not suitable for TIW dosing.

Selected subjects who meet Week 12 transition criteria will transition to the TIW vadadustat dosing regimen at the Week 12 visit. Subjects on 150, 300, 450, or 600 mg of vadadustat daily at the Week 12 visit will transition to an initial vadadustat TIW dose one tablet greater (+150 mg), i.e., 300, 450, 600, or 750 mg vadadustat TIW, respectively. Subjects will be instructed to take vadadustat on dialysis days.

After 2 weeks of treatment in the TIW vadadustat dosing regimen (at Week 14), subjects in any vadadustat TIW dosing arms who have a decline in Hb  $\geq 0.5$  g/dL will be eligible for a dose increase by 1 tablet, based on the investigator's clinical discretion.

Subjects who are not eligible to switch from daily vadadustat to TIW dosing at Week 12 will remain on daily dosing for the remainder of the study.

Subjects on TIW dosing may be converted back to vadadustat once daily dosing at the discretion of the investigator in the setting of inadequate Hb response. The starting daily dose after the switch from TIW to daily dosing will be based on the investigator's discretion after review of the subject's clinical status and dosing history, in particular, the daily dose previously administered to the subject prior to the transition to TIW dosing (Week 12). Subjects who switch from vadadustat TIW to daily dosing will continue once daily vadadustat until the end of the Treatment Period.

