##### **8.4.9.1 RBC Transfusion**

Investigators will use their local institution's transfusion guidelines when determining whether to transfuse a study subject. In general, in the event of an acute or severe loss of blood, a RBC transfusion will be administered as clinically indicated. In less severe instances but where there may be worsening of anemia or moderate to severe symptoms of anemia, RBC transfusions are permitted at the discretion of the investigator given medical necessity. Study drug (vadadustat or epoetin alfa) may be continued during the transfusion period.

Reasons for RBC transfusion will be captured in the appropriate CRF.

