##### **8.4.9.2 ESA Use**

ESA administration will be allowed when medically necessary at the discretion of the investigator. In general, ESA will not be administered in subjects with Hb  $\geq 8.5$  g/dL, and ESA will be stopped when Hb  $\geq 9.0$  g/dL. ESA therapy will be administered using an approved ESA and dosing as per the local institution's guidelines and per the approved product label.

While receiving ESA therapy, subjects randomized to vadadustat must temporarily interrupt vadadustat. A minimum interval will be observed prior to restarting vadadustat after the last dose of ESA, and treatment will be resumed after the following intervals:

- 2 days after last dose of epoetin alfa
- 7 days after last dose of darbepoetin alfa
- 14 days after last dose of methoxy polyethylene glycol-epoetin beta

Following ESA administration, vadadustat will be resumed at the same dose as previously used or with one additional tablet (+150 mg) at the discretion of the investigator.

Reasons for ESA use will be captured in the appropriate CRF.

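### The per-protocol rescue exclusion stops at the start of the evaluation period, and ESA rescue is not defined so that the two arms can be compared

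*Protocol*

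**What the plan says.** **PP set.** Section 11.2 requires study drug during the primary evaluation period, at least one Hb value in it, no major deviation affecting the primary analysis, and that the subject "received no rescue therapy (with ESA or transfusion) prior to the evaluation period". There is one PP definition for all efficacy endpoints: "Efficacy analyses will utilize the Randomized, Full Analysis, and PP Populations".

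**Endpoints.** Section 5.3.1 defines the primary endpoint as "the mean change in Hb between Baseline (average pretreatment Hb) and the primary evaluation period (average Hb from Weeks 10 to 12"). The secondary evaluation period is Weeks 18 to 20 (Section 5.3.2.1). That section also lists ESA rescue and RBC transfusion as endpoints, without naming an arm.

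**Rescue.** On transfusion, Section 8.4.9.1 says: "Study drug (vadadustat or epoetin alfa) may be continued during the transfusion period". On ESA use, Section 8.4.9.2 says: "While receiving ESA therapy, subjects randomized to vadadustat must temporarily interrupt vadadustat". It then gives the waiting times before vadadustat restarts. It has no matching text for the epoetin alfa arm, and Section 7.6.2 lists ESA use as a reason for interruption in the vadadustat arm only. Section 8.4.6 titrates epoetin alfa in steps of about 25%.

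**Transition to three-times-weekly (TIW) dosing.** Section 8.4.5.2 bars subjects rescued for worsening anemia of CKD at any time from Day 1 to Week 12. It does not count as rescue "ESA or RBC transfusion prior to Week 12 for reasons unrelated to worsening of anemia due to CKD".

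**The concern.** A PP set is meant to show what the study drug does when taken as planned. If rescue is grounds for exclusion because it distorts Hb, it distorts Hb most when it falls inside the averaging window, and that is where this criterion stops. For the Weeks 18 to 20 endpoints the gap is wider if the evaluation period in the criterion means the primary one.

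Two further faults concern the word rescue. Sections 11.2 and 8.4.5.2 differ on when it counts and on what it covers. And an ESA is an identifiable rescue in a vadadustat subject, whereas in an epoetin alfa subject more ESA is ordinary titration. A vadadustat subject with falling Hb who gets an ESA before Week 10 leaves PP and counts under ESA rescue; an epoetin alfa subject with the same course who is titrated upward stays in PP and does not count. Both the endpoint and the ESA part of the exclusion then compare unlike things.

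**Working it through.** The protocol gives no rescue rate, power or standard deviation, so there is no stated figure for the effect of rescue to reproduce. The first three steps compare text; the rest size the problem.

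**1. Can a subject rescued in Weeks 10 to 12 meet every PP condition?**
- Rescue before the period: no, so the rescue criterion is met.
- Study drug in the period: met after a transfusion, because study drug may continue. Met after a short ESA course if vadadustat was taken earlier in the window or restarted within it; the stated wait after epoetin alfa is 2 days. Not met if an ESA replaces vadadustat for the whole window.
- Major deviation: permitted rescue is not a deviation. Inadvertent ESA is one (Section 8.5.2) and might be caught here.

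So such a subject can remain in PP.

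**2. Cut-off and meaning.**

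| | Section 11.2 (PP) | Section 8.4.5.2 (TIW) |
|---|---|---|
| Rescue counts | before the evaluation period | Day 1 to Week 12 |
| Unrelated ESA or transfusion | no qualifier | not rescue |

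A subject rescued in Week 11 for worsening anemia is barred from TIW as rescued, yet stays in PP. A subject transfused in Week 5 for a bleed can move to TIW as unrescued, yet on the plain words of 11.2 leaves PP.

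**3. Arms.** The vadadustat arm has an interruption rule and restart rules that mark ESA rescue. The epoetin alfa arm has nothing that separates rescue from a 25% step.

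**4. One subject.** Planned arms: 40 at 3:3:2 gives 15/15/10; 55 at 3:3:3:2 gives 15/15/15/10; 30 at 1:1 gives 15/15. These match the synopsis schematic. One subject moves a proportion by 100/15 = 6.7 or 100/10 = 10 points. A lift of 0.5 to 1.5 g/dL (assumed) in one subject's average moves the mean of an arm of 15 by 0.5/15 = 0.033 to 1.5/15 = 0.10 g/dL.

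**5. Arm mean.** Shift = share affected × lift. As a rough range for the share, Section 4.2 reports withdrawals for worsening anemia in the earlier Phase 2 hemodialysis study: 0 of 30, 1 of 33 (3%) and 6 of 31 (19%). The 10% row is an intermediate assumption.

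| Share | Lift 0.5 | Lift 1.5 |
|---|---|---|
| 3% | 0.015 | 0.045 |
| 10% | 0.05 | 0.15 |
| 19% | 0.095 | 0.285 |

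These values apply if that share of the analysed subjects has a lifted average. In the PP primary analysis only rescue inside the window escapes the criterion. If rescue is spread evenly over 12 weeks, that is 2/12 = one sixth, and the range falls to about 0.015/6 = 0.0025 to 0.285/6 = 0.0475 g/dL.

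**6. Will it occur at all?** Main-study vadadustat subjects: 30 + 45 = 75. The chance of at least one rescue in Weeks 10 to 12 is 1 − (1 − share/6)^75, which gives 31% at 3%, 72% at 10% and 91% at 19%.

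**The case against.** The study is exploratory and descriptive (Sections 11.1 and 11.6), so no test depends on PP. A subject on an ESA throughout Weeks 10 to 12 already fails the dosing condition. Rescue is reported separately and its reasons are recorded. The evaluation period in the PP criterion could be read as whichever period is being analysed, which would narrow the Weeks 18 to 20 gap. The 3 to 19% range comes from withdrawals, not rescues, and the 19% arose on TIW dosing, while Weeks 1 to 12 here are daily dosing; the daily cohorts gave 0% and 3%. All of this stands and limits the severity. It does not close the gap for transfusion or a short ESA course inside either window.

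A reader might infer more, and the documents do not support it:

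- *That the Randomized and FAS analyses credit Hb after rescue to vadadustat and so turn failures into successes.* The FAS asks only that a subject "had at least one Hb assessment during the primary efficacy evaluation period" and received a dose. The protocol says nothing about Hb after rescue. That is commonly left to the SAP, and using all values is a legitimate treatment-policy choice. The primary endpoint is a mean change with no success category. ESA rescue is generally stopped at Hb 9.0 g/dL or above, so alone it rarely reaches 10.0 to 11.0. It could matter for the 0.5 g/dL increase endpoint, chiefly in hyporesponders: a baseline of 8.4 and an average of 9.0 gives 0.6.
- *That PP removes failures from one arm only.* Transfused subjects leave PP in both arms; the imbalance concerns ESA rescue.
- *That ESA rescue is bound to be near zero in the control arm.* It is undefined there, not precluded.
- *That 10 to 20% of vadadustat subjects will be rescued, with as many points of false response.* No document gives such a rate, and the second part needs every rescued subject to cross the threshold.

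**Conclusion.** The point holds and should be fixed, but it is not critical. Three faults rest on stated text: the PP criterion omits rescue inside the period it is meant to protect; Sections 11.2 and 8.4.5.2 disagree on the cut-off and meaning of rescue; and ESA rescue, as an endpoint and as a PP exclusion, is not like for like against a titrated ESA. The firm figure is 6.7 to 10 points on a proportion per affected subject. The shift in the mean depends on an assumed rescue share and lift: 0.015 to 0.285 g/dL over the range shown, and about one sixth of that in the PP primary analysis if rescue is spread evenly.

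**What to change.** 1. In Section 11.2, make the PP criterion *no rescue prior to or during the evaluation period*, applied to each evaluation period analysed.
2. State one definition of rescue for analysis, including whether ESA or transfusion for unrelated reasons counts, and reconcile Section 11.2 with 8.4.5.2 and 8.4.9. This concerns the analysis definition only and takes no position on when rescue should be given.
3. Report ESA rescue descriptively for the vadadustat arms only, and use RBC transfusion as the between-arm rescue measure.
4. Add a sensitivity summary of the mean change that leaves out Hb values after non-study ESA or transfusion.

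The cost is wording in the protocol and the SAP, plus one extra summary. Reasons for rescue are already recorded on the case report form. A few subjects will leave PP, which matters a little in arms of 10 to 15.

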#### **11.4 Disposition of Subjects**

The number and percentage of subjects randomized and included in each analysis population will be summarized by treatment and overall. Reasons for excluding subjects from the analysis populations will be presented in a by-subject listing.

The number of randomized subjects who completed the study, discontinued early from study drug, completed or discontinued from the study, and reasons for discontinuation will be summarized by treatment group and overall.

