## APPENDIX A: SCHEDULE OF ACTIVITIES

Study Period	Screening [a]		Study Treatment Period													Safety Follow-Up	
	SV1	SV2	1	2	3	4	5	6	7	8	9	10	11	12	13	14 [c]	15
Visit	SV1	SV2	1	2	3	4	5	6	7	8	9	10	11	12	13	14 [c]	15
Weeks of study completed			Baseline/ Day 1 [b]	Week 1 Day 8	Week 2 Day 15	Week 4 Day 29	Week 6 Day 43	Week 8 Day 57	Week 10 Day 71	Week 11 Day 78	Week 12 Day 85	Week 13 Day 92	Week 14 Day 99	Week 16 Day 113	Week 18 Day 127	EOT Week 20 Day 141	Week 24 Day 169
Study Day	Day -28 to 0																
Visit Window (Days)	—	—	+5	±3	±3	±3	±3	±3	±3	±3	±3	+5	±3	±3	±3	±3	±5
Administrative Procedures																	
Informed consent	X																
Eligibility criteria [d]	X	X	X														
Review Contraception methods [e]	X	X	X														
Vital Signs [f]	X	X [g]	X [g]	X	X	X	X	X	X	X [g]	X	X	X	X	X [g]		
Demographics, Medical History [h]		X	X [i]														
Physical Exam [j]		X															
12-Lead ECG [k]			X														
Dialysis Adequacy (Kt/V)	X										X					X	
EQ-5D-5L			X								X					X	X
SF-36v2			X								X					X	X
PGI-S			X								X					X	X
PGI-C																	X
Randomization			X														
Assessment for meeting criteria to switch from daily to TIW dosing (vadadustat arm)												X					
Status check [l]																	
Safety Assessments																	

Study Period	Screening [a]		Study Treatment Period													Safety Follow-Up	
	SV1	SV2	1	2	3	4	5	6	7	8	9	10	11	12	13	14 [c]	15
Visit	SV1	SV2	1	2	3	4	5	6	7	8	9	10	11	12	13	14 [c]	15
Weeks of study completed	Day -28 to 0		Baseline/ Day 1 [b]	Week 1 Day 8	Week 2 Day 15	Week 4 Day 29	Week 6 Day 43	Week 8 Day 57	Week 10 Day 71	Week 11 Day 78	Week 12 Day 85	Week 13 Day 92	Week 14 Day 99	Week 16 Day 113	Week 18 Day 127	EOT Week 20 Day 141	Week 24 Day 169
AE review [m]			X	X	X	X	X	X	X	X	X	X	X	X	X	X	X
Review use of rescue therapy (RBC transfusions and ESA therapy)			X	X	X	X	X	X	X	X	X	X	X	X	X	X	X
Review of therapeutic phlebotomy				X	X	X	X	X	X	X	X	X	X	X	X	X	X
Laboratory Evaluations																	
Serum Pregnancy test [n]			X														
CBC [o] [p]	X	X	X [q]	X	X	X	X	X	X	X	X	X	X	X	X	X [q]	
Reticulocyte count			X	X		X		X		X	X	X		X		X	
Folate and vitamin B12	X																
CRP			X									X					X
Serum chemistry [r]	X		X								X						X
LFTs [s]	X		X		X	X	X	X	X		X		X	X	X	X	
Iron indices [t]	X		X			X		X			X			X		X	
Lipid panel [u]			X														X
Biomarkers (VEGF and Hepcidin) [v]			X								X						X

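### The per-protocol population in Section 11.2 excludes rescue only before the primary evaluation period, so subjects rescued within Weeks 10 to 12 can remain with rescue-affected Hb in the average

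*Protocol*

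**What the plan says.** Protocol Section 5.3.1 defines the primary endpoint as the change in Hb from Baseline to "the primary evaluation period (average Hb from Weeks 10 to 12"). Hb is scheduled three times in that period, at the Week 10, 11 and 12 visits (Section 9 and Appendix A).

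Section 11.2 sets four conditions for PP membership:

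- the subject "received study drug during the primary evaluation period";
- there is at least one Hb assessment in that period;
- the subject "received no rescue therapy (with ESA or transfusion) prior to the evaluation period";
- there is no major protocol deviation affecting the primary endpoint analyses. The list of such deviations is kept in a separate document fixed before database lock.

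Rescue is allowed during treatment. Section 8.4.9.2 states that "ESA administration will be allowed when medically necessary at the discretion of the investigator", and Section 8.4.9.1 gives similar discretion for transfusion. Section 11.5 carries the last observation forward for missing Hb. It has no rule for Hb measured after rescue.

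**The concern.** The first two PP conditions refer to what happens during the evaluation period. The rescue condition refers only to what happened before it. Rescue given inside the period is therefore outside the exclusion, although that is the interval in which Hb is averaged for the primary endpoint.

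A subject transfused or given ESA rescue between the Week 10 and Week 12 visits can then count as per-protocol while part of the averaged Hb reflects the rescue and not the assigned drug. Arms are planned at about 10 or 15 subjects, so a single subject has some weight in an arm mean.

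**Working it through.** **Step 1. Does another PP condition remove the subject?**

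| PP condition (Section 11.2) | Met by a subject rescued within Weeks 10 to 12? |
|---|---|
| Study drug taken during the period | It can be. For transfusion, "Study drug (vadadustat or epoetin alfa) may be continued during the transfusion period" (8.4.9.1). For ESA rescue, vadadustat is only interrupted and may resume "2 days after last dose of epoetin alfa" (8.4.9.2). Doses taken in the period before the rescue also count. |
| At least one Hb in the period | Yes. One value is enough. |
| No rescue before the period | Yes. The rescue came later. |
| No major deviation | It can be. Rescue under Section 8.4.9 is permitted and is not in itself among the notifiable deviations in Section 13.2. Inadvertent ESA is a deviation (8.5.2), but that is a different event. |

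So the subject can stay in PP, and nothing in the protocol sets aside the Hb measured after rescue.

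**Step 2. How does the protocol treat rescue elsewhere?** The criteria for moving to three-times-weekly vadadustat (8.4.5.2) bar rescue for worsening CKD anemia from Baseline through Week 12. A vadadustat subject rescued at Week 11 for that reason fails the transition criteria but can remain per-protocol for the Weeks 10 to 12 endpoint.

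**Step 3. How long is the uncovered interval?** This assumes that the evaluation period starts at the Week 10 visit, which the protocol does not say. The nominal length is Day 85 − Day 71 = 14 days. With ±3 days at each visit it runs from 14 − 6 = 8 to 14 + 6 = 20 days.

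**Step 4. Effect of keeping one such subject.** The protocol has no figure of its own to reproduce: it gives no rescue frequency, no Hb effect of rescue and no SD. Arm sizes come from the synopsis schematic and agree with the randomization ratios: 3:3:2 of 40 gives 15, 15 and 10, and 3:3:3:2 of 55 gives 15, 15, 15 and 10. The assumed net rescue effect d is 0 to 1.0 g/dL. It is 0 if a transfusion only replaces lost blood or if an ESA has not yet acted.

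Shift in arm mean = d × (Hb values affected ÷ 3) ÷ n. At d = 1.0:

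| Rescue between visits | Values affected | n = 15 | n = 10 |
|---|---|---|---|
| Week 10 and Week 11 | 2 of 3 | (2/3)/15 = 0.044 | (2/3)/10 = 0.067 |
| Week 11 and Week 12 | 1 of 3 | (1/3)/15 = 0.022 | (1/3)/10 = 0.033 |

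All entries are in g/dL, and each range starts at 0.

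**Step 5. Effect of removing that subject instead.** Let M be the mean of the other subjects and x the subject's own average. The arm mean rises by M − [(n − 1)M + x]/n = (M − x)/n. Assume M = 10.5 (middle of the target range) and x = 8.5 to 9.0 (the levels in 8.4.9.2 that guide starting and stopping ESA rescue), a gap of 1.5 to 2.0 g/dL.

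- n = 15: 1.5/15 = 0.10 to 2.0/15 = 0.13 g/dL.
- n = 10: 1.5/10 = 0.15 to 2.0/10 = 0.20 g/dL.

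If the subject's baseline equals that of the others, the same shift applies to the mean change.

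**The case against.** **The detail may sit elsewhere.** Section 11.3 leaves some population detail to the SAP, and the list of major deviations is a separate document. Either could censor Hb after rescue or add an exclusion. That is possible, but Section 11.2 does not leave the rescue window open. It sets one, and the window misses the interval being averaged. The point is a stated rule with the wrong limit, not an omission.

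**The choice may be deliberate.** Rescue before Week 10 can affect all three values, whereas rescue after the Week 10 visit leaves that value untouched, so dropping the whole subject discards usable data. A reader might infer that PP is declared to be the population showing Hb free of rescue. The protocol states no such purpose; it is only an inference from the presence of a rescue clause. The inconsistency of the time limit with the averaging interval remains either way.

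**Exact day contrasts go too far.** It is tempting to say that a subject rescued the day before the Week 10 visit is removed and one rescued the day after is kept. That requires the period to begin at the subject's actual Week 10 visit. The protocol gives only week numbers and visit windows. If the period opens on a nominal or windowed day, the contrast, the 8 to 20 days and the number of affected values all change.

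**The remedy moves the mean more than the problem does.** On the assumptions above, keeping the subject shifts an arm mean by at most 0.067 g/dL, and removing the subject raises it by 0.10 to 0.20 g/dL. This stands. It is a real cost of excluding on a post-randomization event that marks low Hb, and it limits how much weight PP can carry.

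**Conclusion.** The point holds as a minor defect of wording. The PP definition lets a subject rescued within Weeks 10 to 12 remain, with one or two of three averaged Hb values possibly affected. Under the assumptions in the working, the shift per retained subject is 0 to 0.067 g/dL (n about 10) or 0 to 0.044 g/dL (n about 15).

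A reader might go on to infer that the trial's efficacy conclusion is at risk. The documents do not support that. All efficacy analyses are descriptive, PP is one of three efficacy populations, the Randomized and Full Analysis definitions do not exclude for rescue, and ESA rescue and transfusion are reported as secondary endpoints. Few subjects are likely to be rescued in so short an interval, though the protocol gives no rate.

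**What to change.** In Section 11.2, change only the time limit of the rescue clause, so that it covers ESA or transfusion rescue *prior to or during the primary evaluation period (through the Week 12 Hb assessment)*. Leave the meaning of rescue therapy as it is. Widening the clause to transfusion for any reason would sit badly with Section 8.4.5.2, which does not count ESA or transfusion given for surgery or bleeding as rescue for the transition criteria.

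No new data are needed. Appendix A already has the item "Review use of rescue therapy (RBC transfusions and ESA therapy") at every visit from Baseline, the reasons for rescue are recorded on the CRF, and Section 11.4 provides that "Reasons for excluding subjects from the analysis populations will be presented in a by-subject listing".

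The cost is that a few more subjects leave PP because of a post-randomization event, with the upward shift in the PP mean shown in Step 5. PP should therefore be presented as supportive to the Randomized and Full Analysis results. Leaving out only the Hb values after rescue would keep the subject, but it needs a new data-handling rule. That rule would also have to say whether the values left out count as missing, since Section 11.5 would then carry the earlier value forward.
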